This clinical trial aims to investigate the effectiveness of a Cognitive Behavioural Therapy (CBT) program delivered via a smartphone application (called *ClearlyMe*) for improving mental health outcomes in Australian adolescents (aged 12 to 17 years) with mild to moderate depressive symptoms.

This trial will examine the effectiveness of a new CBT smartphone application (*ClearlyMe*) for reducing depressive symptoms in adolescents when compared to guided use and an active-attention matched control condition.

The primary outcome is depressive symptoms, measured by a change in self-report symptoms between baseline and 6-weeks post-baseline (primary endpoint). Secondary mental health outcomes include improvements in anxiety symptoms, psychological distress and emotional wellbeing between baseline and 6-weeks post-baseline as measured by validated self-report scales. Follow-up outcomes will be evaluated at 4-months post-baseline (secondary endpoint) using the same self-report scales to determine whether effects are sustained in the mid-term and whether the interventions are associated with any delayed benefits or harms.

The primary research questions that this trial seeks to address are:

1. What is the effectiveness of *ClearlyMe* (both self-directed and guided use) for reducing depressive symptoms?

Secondary research questions include:

2. What is the effectiveness of *ClearlyMe* for reducing anxiety symptoms, psychological distress, rumination, and improving emotional wellbeing, quality of life, emotion regulation, and CBT skill acquisition?
3. Does guided support lead to greater engagement with and completion of the *ClearlyMe* app when compared to self-directed use?
4. Do factors such as gender, age, baseline mental health history or symptom severity, perceived need for care or openness to digital mental health, moderate the improvements in depressive symptoms found among users of *ClearlyMe*?
5. Do factors such as rumination, emotion regulation, CBT skill acquisition, digital therapeutic alliance and program engagement/completion mediate the improvements in depressive symptoms found among users of *ClearlyMe*?

Primary and Secondary Hypotheses:

This trial will determine whether the *ClearlyMe* smartphone application is effective for lowering depressive symptoms when compared to guided use and an active attention-matched control in symptomatic adolescents. It is hypothesised that:

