11.1 Assessment of Safety Event Report Forms

Safety reports will be assessed on the seriousness, causality, and expectedness of the event to the trial treatment(s), intervention(s), investigational medical product(s), investigational medical device(s). The following are known and expected adverse effects, harms, risks or discomforts associated with trial procedures, treatments or interventions.

a) Known Adverse Effects

Effect/Event	Criteria
Frequent, current suicidal ideation (i.e., thoughts of death or of harming oneself) detected through the self-report Patient Health Questionnaire-9, at baseline, primary or secondary endpoint.	A participant reports an item score of ≥ 2 (“More than half the days” to “Nearly every day”) on item 9 of the PHQ-9 (i.e., “Over the last two weeks, how often have you had thoughts that you would be better off dead, or of hurting yourself in some way?”)
Action	

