

is unable to be contacted by phone after two attempts, they will be sent an email from the study email address informing them of the attempt to make contact. This email will also contain mental health information and support services.
 
c) A register of these events and associated interactions (i.e., telephone call attempts, times, dates, outcomes) will be recorded in a separate risk management spreadsheet managed by the Trial Manager. These events will also be recorded in the UNSW Safety Monitoring Template.
	
Effect/Event	Criteria

Mental health related hospitalisation reported at primary or secondary endpoint or disclosed in any other study procedures (e.g. call back phone calls, participant emails).
	
Participants reports yes to the item “Throughout the study, have you had any mental health problems where you had to go to a hospital emergency department, or had to stay in hospital for more than one day?” in the primary and secondary endpoint study assessments, or, reports this event via other study procedures and activities.

Action	

All relevant study data for this event will be recorded in the UNSW Safety Monitoring Template for reporting.
	
Effect/Event	Criteria

Self-identified deterioration in mental health due to study activities reported by participants at primary or secondary endpoints.
	
Participants reports yes to the item “At any point throughout the study, did you feel that any of the study activities made your mental health or feelings of depression, anxiety or suicidality worse?” in the primary and secondary endpoint assessments, or, reports this event via other study procedures and activities.

Action	

All relevant study data for this event will be recorded in the UNSW Safety Monitoring Template for reporting.
	

b) Known Harms, Risks or Discomforts

The interventions evaluated in this trial have been designed and reviewed by mental health professionals to support young people to manage their mental health. The researchers do not anticipate significant harm or distress related to use of the interventions in the current trial, however, the following harms, risks or discomforts may occur:

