- a) While CBT is the gold-standard treatment for depression and anxiety, CBT-based activities undertaken in the trial interventions may require emotional effort to complete and have the potential to cause a transient increase in depressive and anxiety symptoms as well as psychological distress (e.g., exposure therapy and behavioural experiments).

- b) While completion of self-report questionnaires about one's mental health have not been shown to increase distress, some participants may experience some emotional discomfort related to being asked about their mental health during the study assessments.

To minimise the potential known harms, risks or discomforts, various safety procedures will be implemented throughout the trial:

- All participants not meeting inclusion criteria at screening, including those deemed ineligible because of severe depressive symptoms and significant suicidality, will be provided with a list of referral services and information on how to access mental health crisis services. This information is provided in Appendix A.
- To mitigate potential discomfort or distress associated with the study assessments, brief youth-friendly versions have been used where possible.
- At the beginning of the study, participants will be advised that the trial interventions are not intended to replace professional medical advice, or to provide crisis support. Participants are also able to seek unlimited mental health treatment and support throughout the study period.
- A list of mental health support services will be provided to participants when completing the study assessments via the "Get Help Now" section of the study assessment websites. This list will also be shown to participants upon completion of each study assessment (see Appendix D).
- Information regarding how participants can contact the research team, how often the trial email is checked, and response time will also be provided in the study welcome email.
- All trial interventions contain emergency help information that can be accessed at any time during the intervention period.

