- Frequent, current suicidal ideation (i.e., thoughts of death or of harming oneself, score greater than 2 on item 9) detected through the self-report Patient Health Questionnaire-9 at primary or secondary endpoint.
- Severe depressive symptoms detected at final study assessment (i.e., secondary endpoint: 4-months post-baseline) through the self-report Patient Health Questionnaire-9.

- Mental health related hospitalisation reported at primary or secondary endpoint or disclosed in any other study procedures (e.g. call back phone calls, participant emails).
- Self-identified deterioration in mental health due to study activities reported by participants at primary or secondary endpoints.

Stopping guidelines

The primary charge of the TMG is to monitor the study for participant safety. As such, the TMG may recommend pausing or terminating the trial if they have concerns for participant safety, based on (but not limited to) a higher than anticipated rate for one or more of the primary endpoints.

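### Two self-report harm items cover the whole study at both 6 weeks and 4 months, so an early event can be recorded twice and a later repeat event is not visible

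*Protocol*

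**What the plan says.** Protocol section 11.1 (Assessment of Safety Event Report Forms, Known Adverse Effects) sets out four events. Two are defined by a yes to a single question:

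- Mental health related hospital care: "Throughout the study, have you had any mental health problems where you had to go to a hospital emergency department", or a hospital stay of more than one day.
- Self-identified deterioration: the item opens "At any point throughout the study, did you feel that any of the study activities made your mental health" and goes on to ask about worsening of that or of specific symptoms.

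The hospital event counts if reported "in the primary and secondary endpoint study assessments, or, reports this event via other study procedures and activities"; the deterioration event has almost the same clause. For both, the only action listed in section 11.1 is to record the relevant study data in the safety template. Neither item, as shown, is limited to the time since the last assessment or asks for a date.

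Appendix I (Safety analyses) lists both among the four primary safety endpoints, the second as "Self-identified deterioration in mental health due to study activities reported by participants at primary or secondary endpoints". Under the same appendix, the Trial Management Group receives monthly safety reports, meets after each assessment round, and may recommend pausing or stopping if an endpoint's rate is higher than anticipated.

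Section 4 says the 4-month follow-up is to establish "whether the interventions are associated with any delayed benefits or harms", and the same sentence names the instruments: "using the same self-report scales to determine whether effects are sustained in the mid-term".

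**The concern.** A question about the whole study, asked twice, gives a cumulative answer the second time. Someone admitted in week 3 correctly answers yes at 6 weeks and yes again at 4 months. Someone admitted in week 3 and again in week 12 gives the same pair of answers. Someone who missed the 6-week assessment stays in the trial (section 9.6), and their 4-month yes could refer to either period.

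Two things are at stake. First, each yes meets the event definition in section 11.1, so one event can enter the register twice, and the Trial Management Group judges safety on rates. Second, a further event in a participant already affected does not show in the item, although hospitalisation is a serious adverse event under Appendices I and J.

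The deterioration item is the more exposed. Section 11.1 warns that the CBT activities "have the potential to cause a transient increase in depressive and anxiety symptoms", and the arm instructions in section 10.1 describe 6 weeks of access. Reports tied to study activities may therefore be concentrated in the first period and be repeated at 4 months.

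**Working it through.** The protocol states no event rate or derived figure on this point, so there is nothing to reproduce. The check is a reading of the possible answer pairs, followed by an illustration on assumed rates.

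**Answer pairs, read literally and with full recall**

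| 6 weeks | 4 months | What the items show |
|---|---|---|
| No | No | No event |
| No | Yes | First event after week 6 |
| Yes | Yes | Early event; a later one may or may not have followed |
| Missing | Yes | An event, period unknown |
| Missing | No | No event |

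The third and fourth rows are the problem. The second row is resolved, because section 10 gives each participant a unique code that appears in all reports, so the answers can be paired.

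**Inputs (all assumed except where stated)**

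- p1: proportion answering yes at 6 weeks.
- p2: proportion with a new event between 6 weeks and 4 months, taken as independent of p1.
- m: share of 4-month responders with no 6-week answer. The 20% used below borrows the attrition to 6 weeks planned in section 8. It would apply at 4 months only if those who missed 6 weeks returned as often as everyone else.

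**Share of 4-month yes answers that only repeat an early event, if the 4-month count is taken without pairing:** p1(1 − p2) / [1 − (1 − p1)(1 − p2)]

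- p1 = 5%, p2 = 5%: 0.0475 / 0.0975 = 49%
- p1 = 10%, p2 = 5%: 0.095 / 0.145 = 66%
- p1 = 5%, p2 = 2%: 0.049 / 0.069 = 71%
- p1 = 10%, p2 = 2%: 0.098 / 0.118 = 83%

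A simpler bench mark, for rare events at a constant rate, is 6 / 17.4 weeks = 34%.

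**Share of 4-month responders for whom a yes could be dated by pairing:** (1 − m)(1 − p1)

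| p1 | m = 0 | m = 20% |
|---|---|---|
| 2% | 98% | 78% |
| 5% | 95% | 76% |
| 10% | 90% | 72% |
| 20% | 80% | 64% |

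With no missed 6-week assessments and independent periods, the share of participants with a late event who had already answered yes is p1 itself. If events recur in the same people, it is larger.

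**Upper bound on undated participants:** 20% of 163 = 32.6, about 33 per arm. This is everyone expected to be missing at 6 weeks. Only those who return at 4 months and answer yes are affected, so the real number is smaller.

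**The case against.** A reader might infer that the 4-month answers cannot show the delayed harms that the trial sets out to detect. The documents do not support that, for three reasons.

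- Section 4 ties that aim to the symptom scales, which are given afresh at each assessment.
- The other two primary safety endpoints are not cumulative. The suicidal ideation item asks "Over the last two weeks, how often have you had thoughts that you would be better off dead", and severe depression is a questionnaire total of 20 or more at 4 months.
- Even for the two items at issue, a no followed by a yes identifies a first late event, subject to recall.

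Whole-study wording also has merit. It recovers early events from people who missed 6 weeks, and it gives a complete ever/never measure, which fits the way Appendix I words both endpoints. Limiting the 4-month question to the time since the last questionnaire could lose early events that a participant did not disclose, or did not attribute to the study, until later.

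Double counting is a risk, not a stated plan. Nothing says that the two assessments will be added together, serious events are classified individually (section 11.3), and events may be disclosed by other routes. The survey layouts are not shown, so a follow-up question on date cannot be ruled out. A SAP may set the reporting rule.

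All of this stands, and it limits the point. It does not remove it: pairing cannot separate the two kinds of yes/yes or date a yes from someone who missed 6 weeks, and no analysis rule can recover timing that was not collected.

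**Conclusion.** The weakness is real but minor to moderate. It affects two of the four primary safety endpoints, and within them only participants with an early event or no 6-week answer. For these, the items alone leave timing unclear, let one event meet the definition twice, and hide a later event after an earlier one.

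It does not defeat the delayed-harm aim. Its size cannot be stated, because the documents give no event rates. The 49% to 83% repeat shares apply only to an unpaired 4-month count, which the protocol does not say it will use; the 34% rests on a constant rate, and the 33 per arm is a ceiling. The conclusion assumes that the items are asked as section 11.1 words them, without a date question in the survey itself.

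**What to change.** Keep the whole-study wording at both assessments. At 4 months, ask anyone who answers yes to either item one follow-up: *Did this happen in the first 6 weeks, after that, or both?* An approximate event date would serve equally well. Asking everyone who answers yes, whether or not they completed the 6-week assessment, resolves the yes/yes and missing/yes pairs without losing events disclosed late.

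Report each item per participant by period (0 to 6 weeks, and 6 weeks to 4 months), and state that each event is entered once in the safety register, with a repeated yes checked against the existing entry.

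The cost is one branching question in the online 4-month survey, with no extra assessment. Participants will misplace some events in time, so the split by period will carry some recall error.

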11.3 Serious Adverse Events

Serious Adverse Events (SAEs) that result in or lead to one or more of the following and the event is **not related** to the trial intervention:

- The death of a trial participant.
- A life-threatening illness or injury involving a trial participant.
- A participant's permanent impairment of body structure or body function.
- In-patient or prolonged hospitalisation (not for a pre-existing condition or an elective surgery) of a trial participant.
- Medical or surgical intervention to prevent life-threatening illness or injury or permanent impairment to a body structure or function of a trial participant.
- Fetal distress, fetal death or congenital abnormality or birth defect.

SAE reports are classified following the safety assessment flowchart and are assessed by Sponsors Independent Medical specified in section 2 of the protocol. The Sponsors Independent Medical cannot delegate this responsibility to other research personnel. SAR reports must be recorded in the [UNSW Safety Monitoring Register Template](#).

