Prior to recruitment commencing, the TMG members will form an understanding of the protocol and study endpoints. The TMG will be provided with a monthly report on safety events and will convene a meeting after the baseline, primary endpoint (6-weeks post-baseline) and secondary endpoint (4-months post baseline) assessments have been completed to review the UNSW Safety Monitoring Template, which includes the number of call backs that were triggered, and the follow-up that was carried out. Meetings will be held face-to-face if practicable, or otherwise by video conference. Prior to each meeting, a report will be sent to the TMG outlining any recommendations and rationales.

Reporting

For this current trial, an adverse event (AE) is defined as any untoward medical or clinical occurrence in a participant without regard to the possibility of a causal relationship. A register of these events and associated interactions will be recorded in a separate risk management spreadsheet managed by the Trial Manager. These events will also be recorded in the UNSW Safety Monitoring Template.

A serious adverse event (SAE) for this trial is defined as any untoward occurrence that involves hospitalisation or death (suicide or otherwise). As per the NHMRC Safety Monitoring and Reporting Guidelines, any suspected unexpected SAEs or reactions will be reported to the TMG and the UNSW Human Research Ethics Committee within 24 hours of the research team becoming aware, using the Adverse Event Form provided by the UNSW HREC. All AEs, both solicited and spontaneous, will be reported to the TMG.

A breach of protocol is defined as something likely to affect the rights and safety of a trial participant (for example, the sharing of data to those outside those with approved access), or the reliability or robustness of the data is compromised. Any serious breaches of protocol will be reported to the TMG and UNSW HREC within 24 hours of the research team becoming aware, using the Suspected Serious Breach Report Form.

Confidentiality

All information and data provided to the TMG will be considered privileged and confidential. The TMG will agree to use these data to accomplish the responsibilities of the TMG and will not use it for any other purpose without written consent from the Chief Investigator or trial sponsor.

Safety analyses

The primary safety endpoints are:

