Appendix J: Standard operating procedures

The MobiliseMe study: Testing different smartphone activities to help improve young people's mental health

Trial Management Group

Version 1 (25th October 2021)

Procedures for eliciting reports of and for recording and reporting adverse event and intercurrent illnesses.

Adverse Events and Serious Adverse Events

For this current trial, an adverse event (AE) is defined as any untoward medical or clinical occurrence in a participant without regard to the possibility of a causal relationship. All AEs will be collected after a participant has consented and enrolled into the trial. AEs may include severe suicidal ideation as reported on baseline, primary or secondary endpoint online self-report assessment. Severe suicidal ideation will be defined as self-reports of suicidal thoughts or thoughts of self-harm More than half the days or Nearly every day, indicated by a score of ≥ 2 on item-9 of the PHQ-9. AEs also include severe depressive symptoms reported by participants at the final assessment (secondary endpoint) before trial ends. Severe depressive symptoms are indicated by a total score ≥ 20 on the Patient Health Questionnaire-9 at secondary endpoint assessment (i.e., 4-months post-baseline). Finally, AE also include mental health related hospitalisation reported at primary or secondary endpoint or disclosed in any other study procedures (e.g. call back phone calls, participant emails).

A serious adverse event (SAE) for this trial is defined as any untoward occurrence that involves hospitalization or death (suicide or otherwise) without regard to the possibility of a casual relationship.

Adverse Reactions (AR) are considered untoward and unintended responses to the trial intervention related to any intervention procedures. AR may include self-identified deterioration in mental health due to study activities reported by participants at primary or secondary endpoints.

Reporting Adverse Events

The trial will maintain a record of any reported adverse events or serious adverse events. A summary of adverse events will be reported to the trial's qualified expert (as named in Section 1). A summary of serious adverse events will be reported annually to the UNSW sponsors delegate and UNSW ethics committee.

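### The safety endpoint named mental health related hospitalisation is met by one yes/no item that also counts emergency-department visits and misses short direct admissions

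*Protocol*

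**What the plan says.** Section 11.1 (Known Adverse Effects) names the event as "Mental health related hospitalisation reported at primary or secondary endpoint or disclosed in any other study procedures". The criterion is a yes to a single item asking whether, during the study, the participant had a mental health problem for which "you had to go to a hospital emergency department, or had to stay in hospital for more than one day". The event is also met if the participant "reports this event via other study procedures and activities". The only listed action is to record the relevant study data in the safety monitoring template.

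Appendix I (Safety analyses) repeats the label, "Mental health related hospitalisation reported at primary or secondary endpoint", as one of four primary safety endpoints. Its stopping guideline lets the Trial Management Group recommend pausing or ending the trial on grounds that include an unexpectedly high rate of any of them. Appendix J states that this group acts in place of a formal data and safety monitoring committee.

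Three places define a serious adverse event (SAE). Section 11.3 lists, among other criteria, "In-patient or prolonged hospitalisation (not for a pre-existing condition or an elective surgery) of a trial participant". Appendix J uses "any untoward occurrence that involves hospitalization or death (suicide or otherwise) without regard to the possibility of a casual relationship". Appendix I uses the same core definition without the causality clause. Neither appendix says what hospitalisation means, and none of the three mentions emergency-department attendance. Appendix J also lists mental health related hospitalisation among its adverse events (AEs).

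**The concern.** The endpoint's name and its criterion describe different things. The item joins an emergency-department visit and a stay of more than one day with an or, and takes one answer for both. The count therefore covers emergency visits and longer stays combined, under a label that a reader will take to mean admissions.

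Two uses of the endpoint suffer. First, the Trial Management Group needs to know what the rate measures before it can judge whether it is higher than expected. A mixture of brief visits and admissions does not tell it that. Second, hospitalisation is one of the features that can make an event serious under this protocol, and a bare yes does not tell the assessor whether an admission took place.

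**Working it through.** The documents state no rate, threshold or expected count for this event, so there is no figure to reproduce and no arithmetic to run. The check sets the item against Section 11.3 for the possible courses of a participant with a mental health problem. The last column is the in-patient or prolonged hospitalisation criterion alone, before its exclusions for pre-existing conditions and elective surgery.

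| Course | Emergency limb | Stay of more than one day | Answer to the item | In-patient or prolonged hospitalisation (11.3) |
|---|---|---|---|---|
| Seen in the emergency department, sent home | met | not met | yes | no |
| Seen in the emergency department, then admitted for any length of stay | met | met or not met | yes | yes |
| Admitted directly, more than one day | not met | met | yes | yes |
| Admitted directly, one day or less | not met | not met | no | yes |

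1. The first row is a yes without an admission: the item is broader than its label.
2. The last row is an admission with a no: the item is also narrower than its label. A short stay reached through the emergency department is still caught, so only direct short admissions are missed.
3. The first three rows give the same answer, so the answer does not show which course occurred.
4. Is there a later step that separates them? For frequent suicidal ideation and for severe symptoms at the final assessment, Section 11.1 offers a call-back from a psychologist. For this event it lists recording only. Disclosure by another route could supply detail in individual cases, but nothing in the text shown makes that systematic.
5. Does the contrast hold against every SAE definition? It is explicit against Section 11.3, which says in-patient. Against Appendices I and J it rests on the ordinary meaning of hospitalisation, because they leave the word undefined.
6. Appendix J contains a related inconsistency: it lists mental health related hospitalisation as an AE, while its SAE definition takes in any untoward occurrence involving hospitalisation. The text does not say how the two fit together.

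**The case against.** The strongest case on the other side is that broad capture is sensible for safety surveillance, that over-counting is the cautious direction, that the same item is put to all arms, and that classification is a separate step. Much of this stands, and it rules out several stronger readings.

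- **A reader might infer that a yes makes an event an SAE.** The documents do not say so. Section 11.1 has safety reports assessed for seriousness, causality and expectedness, and Section 11.3 assigns SAE reports to the sponsor's independent medical expert, who may not delegate the task.
- **A reader might infer that the item could trip a stopping rule or make a published rate wrong by some factor.** The stopping guideline has no numerical threshold and is not confined to these rates. The protocol does not commit to publishing a rate under this label. The share of yes answers that are visits without admission is not given, so no inflation factor can be supported.
- **A reader might infer that the two components can never be separated.** Appendix D, which holds the assessment measures, and the safety flow chart are not available here. A follow-up question or verification step cannot be excluded.
- **A reader might infer that emergency visits without admission are never serious.** Section 11.3 also lists life-threatening illness or injury and intervention to prevent it, and an event treated without admission could meet those criteria.

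None of this removes the mismatch between label and item. Broad capture does not require a combined answer: two questions capture everything the present item does and add the short direct admission. The expert assessment is only as good as the information that reaches it.

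**Conclusion.** The point holds as a mismatch between the name of a primary safety endpoint and the item that scores it. Followed as written, the count mixes emergency visits with admissions and omits direct admissions of one day or less. The Trial Management Group cannot read it as a hospitalisation rate, and the answer alone does not inform SAE classification.

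The size cannot be stated from the documents. It depends on how many yes answers are visits without admission and how many short direct admissions go unasked, and neither is given. The omission is probably the smaller of the two errors if most admissions pass through an emergency department, which is an assumption.

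The conclusion rests on the item being the main source of this endpoint and on there being no separating question in Appendix D. If Appendix D contains one, only the inconsistent wording remains. This is a weakness in data capture and definition that is worth correcting because the correction is cheap. It does not show that the trial's safety classification is wrong.

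**What to change.** At both follow-up assessments (6 weeks and 4 months), replace the combined item with two questions: whether the participant attended a hospital emergency department for a mental health problem, and whether the participant was admitted to hospital for one, for any length of stay. Report each separately under its own name, and keep the label hospitalisation for the second.

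Reconcile the wording of the criterion in Section 11.1, the SAE criterion in Section 11.3, and the definitions and endpoint list in Appendices I and J. This includes the Appendix J listing of the event as an AE alongside an SAE definition that covers any hospitalisation. Leave SAE classification to the full set of Section 11.3 criteria and the existing expert assessment; the amendment should not state that only admissions can be serious.

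The cost is one extra question at two online assessments and a wording amendment.
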